GI30	Constipation/bowel obstruction			SK11	Rash/desquamation		
GI60	Stomatitis/pharyngitis			SK90	Alopecia		
GU00	Incontinence			SX00	Libido loss		
GU03	Urinary frequency/urgency			SX60	Erectile impotence		
HE00	Leukopenia			Other Toxicities (specify):			
HE30	Neutropenia/granulocytopenia			<hr/> <hr/> <hr/>			
ME31	Hyperglycemia			<hr/> <hr/> <hr/>			
MS00	Muscle weakness (not neuro)			<hr/> <hr/> <hr/>			

* Treatment Relation codes: 1-unrelated

2-unlikely

3-possible

4-probable

5-definite

Comments: (Please explain any "other" adverse events reported above, e.g., PA99 Pain-other)

3/15/2006

27242

SOUTHWEST ONCOLOGY GROUP

FOLLOW UP FORM

Page 1 of 1

SWOG Patient ID

SWOG Study No. S

Registration Step

Patient Initials _____ (L, F M)

Institution / Affiliate _____ Physician _____

Participating Group: Group Name/Study No./Patient ID _____ / _____ / _____

Instructions: Please submit at each follow up after completion of treatment until relapse or progression, at time of relapse or progression, and at protocol-specified intervals after relapse or progression. Also submit at time of diagnosis of second primary. All dates are MONTH, DAY, YEAR. Answer all questions and explain any blank fields or blank dates in the **Comments** section. Place an **X** in appropriate boxes. Circle AMENDED items in red.

VITAL STATUS

Vital Status: Alive Dead Date of last contact or death: / /

If vital status is Dead, complete and submit Notice of Death form.

DISEASE FOLLOW UP STATUS

Has the patient had a documented clinical assessment for this cancer (since submission of the previous follow-up form)?

No Yes If Yes, Date of Last Clinical Assessment: / /

NOTICE OF FIRST RELAPSE OR PROGRESSION

Has the patient developed a first relapse or progression that has not been previously reported?

No Yes If Yes, Date of Relapse or Progression: / /

Site(s) of Relapse or Progression: _____

NOTICE OF NEW PRIMARY

Has a new primary cancer or MDS (myelodysplastic syndrome) been diagnosed that has not been previously reported?

No Yes If Yes, Date of Diagnosis: / /

New Primary Site: _____

NON-PROTOCOL TREATMENT

Has the patient received any non-protocol cancer therapy (prior to progression/relapse) not previously reported?

No Yes If Yes, Date of First Non-Protocol Therapy: / /

Agent Name(s): _____

LONG TERM ADVERSE EVENT

[figure not shown]
Has the patient experienced (prior to treatment for progression or relapse or a second primary, and prior to non-protocol treatment) any severe (grade ≥ 3) long term toxicity that has not been previously reported?

No Yes If Yes, Adverse Events and Grades: _____

Comments:

64587

9/15/2003

SOUTHWEST ONCOLOGY GROUP
OFF TREATMENT NOTICE

Page 1 of 1

SWOG Patient ID

--	--	--	--	--	--

SWOG Study No. S

--	--	--	--	--

Registration Step

--

Patient Initials _____ (L, F M)

Institution / Affiliate _____ Physician _____

Participating Group: Group Name/Study No./Patient ID _____ / _____ / _____

Instructions: For each registration step, submit this form within 2 weeks after completion (or discontinuation) of treatment.

Systemic Therapy: List regimens, start and end dates. For multidrug regimens, do not list individual drugs separately; end date would be the date all drugs in the regimen were discontinued.

Surgery: List type of surgery, and in the "end date" column, the date of surgery.

Radiation: List sites, start and end dates (inclusive of boosts and implants).

All dates are **MONTH, DAY, YEAR**. Explain any blank fields or blank dates in the **Comments** section.

Place an **X** in appropriate boxes. Circle **AMENDED** items in red.

Treatment Start Date

Treatment End Date

Regimen or Procedure or Site(s)

_____	_____	_____
_____	_____	_____
_____	_____	_____
_____	_____	_____
_____	_____	_____

(If more room is needed, please continue on a separate page)

Off Treatment Reason (select one):

- Treatment completed per protocol criteria
- Medically required, due to toxicity, specify: _____
- Patient refused, due to toxicity, specify: _____
- Patient refused, other than toxicity, specify: _____
- Progression or relapse. Sites: _____
- Death (submit Notice of Death form)
- Other, specify: _____

Off Treatment Date

Date of completion, progression, death or decision to discontinue therapy:

--	--	--	--	--	--

 /

--	--	--	--	--	--

 /

--	--	--	--	--	--

Will patient receive further treatment?

- No Yes, specify: _____
- Unknown

Date of Last Contact (or death):

--	--	--	--	--	--

 /

--	--	--	--	--	--

 /

--	--	--	--	--	--

Vital Status: Alive Dead (submit Notice of Death form)

Comments:

8756

9/1/2003

SOUTHWEST ONCOLOGY GROUP
NOTICE OF DEATH

Page 1 of 1

SWOG Patient ID

Most Recent SWOG Study No. S

Patient Initials _____ (L, F M)

Institution / Affiliate _____ Physician _____

Participating Group: Group Name/Study No./Patient ID _____ / _____ / _____

Instructions: Answer all questions and explain any blank fields or blank dates in the **Comments** section.

Place an **X** in appropriate boxes. Circle **AMENDED** items in red.

Date of Death: / / (month / day / year)

CAUSES OF DEATH

Any cancer (select one):

No Primary Cause Contributory Possible Unknown

If cancer was the primary cause or if cancer possibly or definitely contributed to death, and the patient had had multiple tumor types, specify those which were causes of death:

Cancer of most recent SWOG study, specify cancer: _____

Cancer of other SWOG study, specify cancer: _____

Other cancer, specify: _____

Toxicity from disease related treatment (select one):

No Primary Cause Contributory Possible Unknown

If Primary Cause, Contributory or Possible, specify treatment and toxicity:

Non-cancer and non-treatment related causes (select one):

No Primary Cause Contributory Possible Unknown

If Primary Cause, Contributory or Possible, specify:

Autopsy? No Yes Unknown

Source(s) of death information:

- Autopsy report
- Medical record / Death certificate
- Physician
- Relative or friend
- Other, specify: _____

Comments:

49467

9/1/2003

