5.0 ELIGIBILITY CRITERIA

Each of the criteria in the following section must be met in order for a patient to be considered eligible for registration. Use the spaces provided to confirm a patient's eligibility. For each criterion requiring test results and dates, please record this information on the Prestudy Form and submit to the Data Operations Center in Seattle (see Section 14.0). Any potential eligibility issues should be addressed to the Data Operations Center in Seattle at [name] prior to registration.

SWOG Patient No. _____

Patient's Initials (L, F, M) _____

- ____ 5.1 All patients must have a histologic diagnosis of adenocarcinoma of the prostate and must be considered to have **clinically localized disease (Stage T1-T3, N0, M0)**, and be considered operable for cure by their primary urologic surgeon.

Patients must have had a radical prostatectomy within 120 days prior to registration **and must fulfill one or more** of the following criteria (from pathologic analysis of the radical prostatectomy specimen) **check all that apply:**

- ____ a. Pathologic Gleason's sum of equal or greater than 8.
- ____ b. pT3b (seminal vesicle) or pT4 or N1.
- ____ c. Pathologic Gleason's sum of 7 and positive margin.
- ____ d. Patients who have either a preoperative serum PSA value of > 15 ng/ml, or a biopsy Gleason score > 7, or a serum PSA level of > 10 ng/ml and a biopsy Gleason score > 6 are eligible.

- ____ 5.2 Serum testosterone must be obtained within 28 days prior to registration.
- ____ 5.3 Patients must have a performance status of 0 - 1 by Southwest Oncology Group criteria (see Section 10.3).
- ____ 5.4 Prior neoadjuvant hormonal therapy (of ≤ 4 months duration) prior to radical prostatectomy is allowed provided that the patient has fulfilled the clinical eligibility criteria prior to hormonal treatment. Patients may have started hormonal therapy post-prostatectomy but prior to registration to this study (see Sections 5.2 and 5.5 for other requirements).

No other therapy aimed at the treatment of this diagnosis may have been given or may be planned while the patient is receiving protocol treatment. The use of low dose megace (< 40 mg/day) for the treatment of hot flashes is allowed.

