7.3 Arm 1 - Hormonal therapy

- a. Zoladex 10.8 mg depot given subcutaneously once every 3 months (13 weeks) for a total of 8 injections given over 2 years, concurrent with Casodex 50 mg orally once daily everyday for two years.
- b. Neo-adjuvant or adjuvant hormonal therapy started prior to registration may be counted as protocol treatment if it included an LHRH agonist (e.g., goserelin acetate, leuprolide acetate, triptorelin) and there was no interruption in treatment. This could be either an LHRH agonist alone or in combination with antiandrogen, but antiandrogen alone will not be counted as pre-registration protocol treatment. Patients must receive a total of 2 years of treatment with LHRH agonist, where the treatment duration of any LHRH agonist received prior to registration may be counted as part of the 2 years of protocol treatment only if that treatment duration was continuous up to the date of registration. It is recommended that patients also complete 2 years of concurrent antiandrogen treatment, but if LHRH agonist was started alone prior to registration the duration of antiandrogen treatment can be shortened to the remaining time of hormonal deprivation after starting the protocol. For patients beginning LHRH agonist prior to registration, every effort should be made to conform to the LHRH agonist administration schedule that is specified in the study calendar, which may mean administering a few doses of single-month depot at the beginning to get on track. All prior hormonal therapy must be documented on the S9921 Local Prostate Carcinoma Prestudy (Form # 23968).

Treatment Schedule

Agent	Dose	Route	Days	ReRx Interval
LHRH Agonist: Goserelin acetate (Zoladex®)	10.8 mg	SC	1	q 3 months (13 weeks) x 8
Anti-androgen: Bicalutamide (Casodex®)	50 mg	Oral (once daily)		1-730 (2 years)

All continuous hormonal treatment counts towards protocol treatment.

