- 11.5 In addition to the study monitoring mentioned above, three formal interim analyses will be done. The decision to terminate accrual early will be made by the DSMC, and will consider disease-free survival, toxicities, and other factors in addition to survival. Additionally, the Southwest Oncology Group Statistical Center will closely monitor throughout the trial whether there is differential use of optional radiotherapy between the two treatment groups and this information will be provided to the DSMC at regular intervals.
- 11.6 The first formal interim analysis will be done after 700 patients have been entered, approximately 6 years after the study opens. Evidence suggesting early termination of the trial would be if the alternative hypothesis of a 30% improvement in survival with the MP + CZ combination arm is rejected at the 0.005 level, using an extension of the logrank test that allows for testing a relative risk not equal to 1. In addition, the null hypothesis of no difference in survival will be tested at the one-sided level of 0.005. The second interim analysis will be performed after 50% of the total expected deaths (275 deaths) will have occurred. Testing will be done as above at the 0.005 level. A third interim analysis will be performed 2.5 years after accrual has been completed. This testing will also be done at the alpha=0.005 level. The final analysis will be performed at the 0.045 significance level, approximately 4 years after accrual has been completed.
- 11.7 Secondary analyses will also be done regarding disease-free survival and toxicities. With 680 patients per arm, toxicity rates can be estimated to within at \pm 4% (95% confidence interval).

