Did the patient receive hormonal therapy after radical prostatectomy but prior to S9921 registration?

No Yes, description: _____

Did the prior hormonal therapy include an LHRH analog?

No Yes, description: _____

Date of first treatment with LHRH analog:

--	--

 /

--	--

 /

--	--	--	--

Date of most recent LHRH analog injection:

--	--

 /

--	--

 /

--	--	--	--

Specified dose duration of most recent LHRH analog injection: _____

1 month 3 month 4 month Other, specify _____

Was LHRH analog treatment continuous from first administration to S9921 registration?

Yes No, explain _____

Did the patient receive any prior radiation therapy in the treatment of this cancer (MUST be No for patient to be eligible)? No Yes

LABORATORY VALUES

PSA value prior to radical prostatectomy:

--	--	--	--	--	--

.

--

 ng/ml

Date of PSA prior to radical prostatectomy:

--	--

 /

--	--

 /

--	--	--	--

PSA value after radical prostatectomy (prior to the start of post-surgical hormone therapy if already started OR within 28 days prior to registration if post-surgical hormone therapy not already started):

--	--	--	--	--

.

--

 ng/ml

Date of PSA after radical prostatectomy:

--	--

 /

--	--

 /

--	--	--	--

Testosterone:

--	--	--	--

 ng/dl (within 28 days prior to registration) Testosterone ILLN:

--	--	--	--

 ng/dl

Date of testosterone:

--	--

 /

--	--

 /

--	--	--	--

If patient had prior hormonal therapy, testosterone value prior to therapy:

--	--	--	--

 ng/dl

Date of testosterone:

--	--

 /

--	--

 /

--	--	--	--

Comments:

3/15/2006

**SOUTHWEST ONCOLOGY GROUP
S9921 PSA REPORTING FORM**

Page 1 of 1

SWOG Patient ID

SWOG Study No. S 9 2 1

Registration Step 1

Patient Initials _____ (L, F M)

Institution / Affiliate _____

Physician _____

Participating Group: Group Name/Study No./Patient ID _____ / _____ / _____

Instructions: Include all measurements of PSA taken since the last reported form. See the Study Calendar (Section 9.0) for collection schedules of PSA. Note PSA measurements taken prior to S9921 registration on the S9921 Prestudy form. All dates are MONTH, DAY, YEAR. Explain any blank fields or dates in the **Comments** section. Please mark **AMENDED** data in red and write **AMENDED** at the top of the form.

PSA

Date of assessment(s)

1. / /

PSA value(s) (ng/ml)

.

2. / /

.

3. / /

.

4. / /

.

5. / /

.

6. / /

.

Comments:

SOUTHWEST ONCOLOGY GROUP
S9921 TESTOSTERONE REPORTING FORM

Page 1 of 1

SWOG Patient ID

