Instructions: **Arm 1** - Please complete this form and submit after every 3 months of protocol hormonal therapy.

Arm 2 - Please complete and submit this form after the 3rd and 6th cycles of chemotherapy (1 cycle = 21 days) summarizing all cycles in the reporting period. Continue to complete and submit this form every 3 months while on protocol hormonal therapy.

Report all adverse events observed. Document the worst Grade seen during the reporting period. Do not code a condition existing prior to registration as an adverse event unless it worsens. Category lists may not include all adverse events from that category.

Record any observed adverse events not listed on the blank lines at the end. All dates are MONTH, DAY, YEAR. Explain any blank dates or fields in the **Comments** section. Place an in appropriate boxes. Circle **AMENDED** items in red and write **AMENDED** across top of form.

TOXICITY Were toxicities assessed during this time period?

No Yes Date of most recent toxicity assessment: / /

Mark box if toxicities were assessed but none were seen. Otherwise indicate grades below.

CTC 2.0 Code	Toxicity	Grade (1 - 5)	Treatment Relation*	CTC 2.0 Code	Toxicity	Grade (1 - 5)	Treatment Relation*
CA50	Hypertension			MS31	Arthritis		
CA51	Hypotension			NR12	Anxiety/agitation		
EN20	Gynecomastia			NR13	Depression		
EN30	Hot flashes			NR60	Sensory neuropathy		
FL30	Sweating			NR92	Insomnia		
FL40	Fatigue/malaise/lethargy			PA00	Headache		
GI00	Nausea			PA30	Abdominal pain/cramping		
GI10	Vomiting			PA40	Chest pain, not cardio or pleur		
GI20	Diarrhea without colostomy			PA99	Pain - other		

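### Adverse event coding starts at registration, but counted hormone treatment can start earlier, so absolute hormone-toxicity rates may be understated by an amount the documents do not fix

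*Combined protocol and SAP*

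**What the plan says.** - **Coding rule.** The instructions on Form #27242 (Section 18.8) read: "Do not code a condition existing prior to registration as an adverse event unless it worsens". They apply to both arms and ask for the worst grade in each reporting period.
- **Eligibility.** Section 5.4 states: "Patients may have started hormonal therapy post-prostatectomy but prior to registration to this study". It also allows up to 4 months of hormones before surgery. Section 5.1 allows up to 120 days between prostatectomy and registration.
- **What counts as treatment.** Section 7.3b states: "Neo-adjuvant or adjuvant hormonal therapy started prior to registration may be counted as protocol treatment if it included an LHRH agonist". The therapy must also have been uninterrupted up to registration; antiandrogen alone does not count. Section 7.4a applies the same hormone guidelines to Arm 2.
- **Toxicity analysis.** Objective 1.2 is a between-arm comparison of toxicity. Section 11.7 adds estimation: "With 680 patients per arm, toxicity rates can be estimated to within" 4 points either way, as a "95% confidence interval". It mentions no split or adjustment for earlier hormone use.
- **Baseline data.** The Prestudy form (Form #23968, Section 18.3) asks: "Did the patient receive hormonal therapy after radical prostatectomy but prior to S9921 registration". It also asks about hormones before surgery, LHRH dates and continuity. It asks for no baseline symptom grades.

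**The concern.** A rule that leaves out pre-existing conditions assumes that baseline comes before treatment. For men admitted on hormones, baseline here can fall inside counted treatment. Four months before surgery plus 120 days after is about 8 months, so up to roughly a third of the 24 months could lie before registration if therapy was continuous. The exposure in that period is credited. Hot flashes, libido loss or gynecomastia that arose in it and stayed at the same grade are not recorded as toxicity, and with no baseline grades on the Prestudy form they cannot be recovered.

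At stake are the absolute rates of hormone toxicity that Section 11.7 sets out to estimate. As reported, they would depend partly on how many men happened to start hormones early. A smaller effect on the arm comparison is also possible.

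**Working it through.** **1. The plan's own figure.** Half-width = 1.96 x sqrt(p(1 - p)/n). With n = 680 and the worst case p = 0.5: 1.96 x sqrt(0.25/680) = 3.76 points. The stated 4 points is reproduced.

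**2. Formula for the understatement.** Let p be the true rate, f the share of men pretreated, and q the share of affected pretreated men whose condition was present at registration and never worsened.

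Coded rate = p x (1 - f x q), so understatement = p x f x q.

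The documents give p for bicalutamide plus an LHRH analog (Section 3.1b): hot flashes 53%, gynecomastia 9%, breast pain 6%. I assume these rates carry over to this population. The documents give neither f nor q, so both are varied.

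**3. When the understatement exceeds 4 points.** This needs f x q above 4/p:

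- hot flashes: 4/53 = 7.5%
- gynecomastia: 4/9 = 44%
- breast pain: 4/6 = 67%

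For hot flashes, 7.5% means f above about 15% at q = 0.5, or about 30% at q = 0.25.

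**4. Size over assumed ranges** (percentage points, q = 0.25 to q = 1)

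| f | Hot flashes (53%) | Gynecomastia (9%) | Breast pain (6%) |
|---|---|---|---|
| 5% | 0.7 to 2.7 | 0.1 to 0.5 | 0.1 to 0.3 |
| 10% | 1.3 to 5.3 | 0.2 to 0.9 | 0.2 to 0.6 |
| 20% | 2.7 to 10.6 | 0.5 to 1.8 | 0.3 to 1.2 |
| 30% | 4.0 to 15.9 | 0.7 to 2.7 | 0.5 to 1.8 |
| 50% | 6.6 to 26.5 | 1.1 to 4.5 | 0.8 to 3.0 |

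The 4 points is a worst-case sampling error. The half-width at an effect's own rate is smaller: 2.2 points at 9% and 1.8 points at 6%. On that yardstick the thresholds for f x q are 24% for gynecomastia and 30% for breast pain.

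**5. The arm comparison.** Randomisation takes place at registration (Section 6.1) and the coding rule is common, so f and q should be similar in both arms apart from chance. Then:

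expected coded difference = (p2 - p1) x (1 - f x q).

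If p1 = p2 this is zero. A true difference of 5.0 points becomes 5.0 x 0.9 = 4.5 at f x q = 10%, and 5.0 x 0.7 = 3.5 at f x q = 30%.

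The equal-q assumption can fail for an effect that chemotherapy aggravates, such as fatigue. A worsened condition is coded in Arm 2 while the same stable condition in Arm 1 is not. With equal true any-grade rates p, the coded difference is then p x f x (q1 - q2), where q1 and q2 are the values of q in Arms 1 and 2. The documents give no values for these.

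**The case against.** The strongest reply is that the toxicity objective is comparative and registration is the point of randomisation. That makes it a defensible baseline, and a rule common to both arms leaves the null intact for effects that behave alike. This stands, and it is why the concern is about absolute rates first.

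A reader might infer that hormone toxicity rates are understated by more than the 4 points in Section 11.7. The documents do not support that. It needs values of f and q that they do not contain; for hot flashes the plausible range lies on both sides of 4 points, and for gynecomastia or breast pain very high values are needed. Setting q to 1 would also overlook that Form #27242 codes worsening, and that an antiandrogen effect first appearing on study in a man pretreated with an LHRH agonist alone is new and can be coded. Nor is the 4 points a claim about completeness of ascertainment.

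Reach is a further limit. Form #27242 is dated 3/15/2006 and came in when a flow sheet was replaced; the flow sheet's coding rule is not shown. Accrual closed on January 12, 2007. EPP sites submit their own toxicity form (Appendix 19.2). How much of the trial's data the instruction governs is therefore unknown.

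None of this removes the mismatch. Where the form was followed, stable effects from counted treatment go uncoded, and Section 11.7 promises estimated rates as well as a comparison.

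**Conclusion.** The point holds as a conditional one. The start of coding and the start of counted treatment disagree for men pretreated with a continuous LHRH agonist, and the disagreement can only lower absolute hormone-toxicity rates. The size is p x f x q with f and q unknown: possibly several points for hot flashes (2.7 to 10.6 at an assumed f of 20%), and at most 1.8 points for gynecomastia at the same f. Between arms, the null is preserved for effects that behave alike, and a true difference is diluted by about (1 - f x q).

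These figures rest on the Section 3.1b rates applying here, on similar f and q in the two arms, and on sites having used Form #27242 as written. This is a cheap improvement to reporting. It does not undermine the randomised toxicity comparison.

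**What to change.** In Section 11.7, keep the toxicity comparison in all randomised patients as the between-arm analysis. Add a table of hormone-related toxicity rates by arm, separately for men with and without hormonal therapy before registration, taken from Form #23968. Use the rates in hormone-naive men when stating absolute incidence, and say that rates in pretreated men omit effects already present and stable at registration. Report the share pretreated in each arm, which supplies f.

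No new data are needed, since Section 7.3b already requires prior hormones to be documented on that form. The cost is precision: if half of 680 are hormone-naive, the half-width is 1.96 x sqrt(0.25/340) = 5.3 points instead of 3.76. Hormone-naive men may also differ from pretreated men in other ways, so their rates should be labelled as applying to that group.

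Two further changes might suggest themselves, and I would make neither. Moving the form's baseline to the first counted hormone dose would credit symptoms from before randomisation to the assigned arm and would need retrospective grading. Making the hormone-naive subgroup the main arm comparison would give up the randomised population for little gain.
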